9. Any other disorder that may interfere with the results of the efficacy endpoints.
10. Pregnancy or breastfeeding.
11. Currently taking another investigational drug for any condition or any therapeutic drug for Gaucher disease.
12. The subject and/or subject's parent(s) or legal guardian(s) are unable to understand the nature, scope, and possible consequences of the study.
13. Medical history of any food/drugs allergy.

TEST PRODUCT(S), DOSE AND MODE OF ADMINISTRATION: Taliglucerase alfa, 60 units/kg, intravenously, every 2 weeks

DURATION OF TREATMENT: 12 months

DISCONTINUATION FROM THE STUDY:

Reasons for permanent discontinuation include the following:

- The subject experiences two or more Grade 3 toxicities or one or more Grade 4 toxicity considered by the Investigator associated with taliglucerase alfa treatment
- A subject who experiences progressive hypersensitivity or severe hypersensitivity will be treated appropriately and may be withdrawn from the study, at the discretion of the treating Investigator and/or Medical Monitor

- The subject, or subject's parent or guardian, requests to discontinue treatment
- Investigator feels that it is not in the best interest of the subject to continue treatment and/or the Investigator believes that the subject can no longer be compliant with the requirements of the study
- Deteriorating clinical condition, for which the Investigator decides additional treatments would be needed

EFFICACY VARIABLES:

Primary efficacy variable is:

- Percent change in spleen volume (expressed in MN) from baseline to Month 12

Secondary efficacy variables are:

- Percent change in liver volume (expressed in MN) from baseline to Month 12
- Percent change in hemoglobin from baseline to Months 3, 6, 9, and 12
- Percent change in platelet count from baseline to Months 3, 6, 9, and 12
- Percent change in Lyso-Gb1 from baseline to Months 3, 6, 9, and 12
- Percent change in Chitotriosidase from baseline to Months 3, 6, 9, and 12

Other efficacy variables are:

- Change in height SDS (standard deviation score) from baseline to Months 3, 6, 9, and 12
- Change in weight SDS from baseline to Months 3, 6, 9, and 12
- Change in Tanner Stage from baseline to Month 12
- Change in bone age (by X-ray of left hand and wrist) from baseline to Month 12
- Change in bone mineral density (DEXA) from baseline to Month 12

Exploratory endpoints:

- Change in mSST from screening, Month 6 and 12.

SAFETY ENDPOINTS:

- Adverse events

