6.3.3 Removal of Subjects from Study

Reasons for permanent discontinuation include the following:

1. The subject experiences two or more Grade 3 toxicities or one or more Grade 4 toxicity considered by the Investigator associated with taliglucerase alfa treatment (see [Section 8.2.1: Adverse Events](#); and [Appendix 14.5: WHO Common Toxicity Criteria](#))
2. The subject experiences progressive hypersensitivity or severe hypersensitivity will be treated appropriately and may be withdrawn from the study, at the discretion of the treating Investigator and/or Medical Monitor (see [Appendix 14.2: Infusion Rate Algorithm](#); and [Appendix 14.3: Taliglucerase Alfa Hypersensitivity Evaluation and Treatment Algorithm](#))
3. The subject, or subject's parent or guardian, requests to discontinue treatment
4. Investigator feels that it is not in the best interest of the subject to continue treatment and/or the Investigator believes that the subject can no longer be compliant with the requirements of the study
5. Deteriorating clinical condition, which the Investigator decides additional treatments would be needed

For any discontinuation, the Investigator will obtain all required details and document the date and the main reason for the premature discontinuation. If the reason for discontinuation is an adverse event, the specific event or the main laboratory abnormality will be recorded in the case report form (CRF). The Investigator will make thorough efforts to document the outcome. The Investigator will attempt to continue to follow the subject for the full duration of the study or at least for 30 days following discontinuation. If circumstances prevent the subject from completing all visits, every attempt will be made to complete all procedures listed in [Section 9.2.11](#) for Visit 27.

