9.2.12 Early Termination Visit

If the subject withdraws or is discontinued from the study before completion, the reason for discontinuation must be documented in the subject's CRF. Whenever a subject is discontinued, the procedures/assessments listed in [Section 9.2.11](#) should be conducted, unless advised otherwise by the Medical Monitor.

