14.2 Appendix 2: Infusion Rate Algorithm

[figure not shown]
The infusion rate (IR) may be adjusted according to individual subject symptoms and signs. The assumptions with respect to adverse experiences to the infusion are:

1. Most of the subjects will tolerate the infusion without any special symptom or event. The infusion rate may be increased over time to the maximal rate 2.0 mL/minute (or 120 mL/hour) only after discussion with the Medical Monitor (an infusion duration of 1 hour).
2. Subjects presenting symptoms and signs of **severe** hypersensitivity will be evaluated according to the WHO Drug Toxicity criteria and there may be a discontinuation of treatment according to the protocol.
3. Subjects may present signs and symptoms that will respond to reducing of the infusion rate and may not appear at the next infusion.
4. Tolerability and the subject specific infusion rate will be assessed and decided by the Investigator according to vital signs and clinical status of the subject.

Definitions to be applied regarding tolerability of infusions are as follows:

Good Tolerability	Partial Tolerability	Poor Tolerability
Infusion was performed without signs and symptoms (such as burning, pruritus, flushing, discomfort, or change in vital signs).	Signs and symptoms appeared during the infusion and resolved after slowing infusion rate or at the end of the infusion.	Signs and symptoms meeting the definitions of WHO Grade 1 or 2 toxicity responding to reduction of infusion rate or responding to treatment (example, antihistamine for urticaria).

The specific algorithm to be followed is below.

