14.3 Appendix 3: Taliglucerase Alfa Hypersensitivity Evaluation and Treatment Algorithm

During and after infusion of taliglucerase alfa, the following algorithm will be followed to monitor and manage the occurrence of hypersensitivity, anaphylaxis, or anaphylactoid reactions.

Clinical Signs

Early

- Sensations of warmth and itching
- Feelings of anxiety or panic

Moderate

- Pruritus
- Flushing
- Urticaria
- Chest discomfort
- Mild hypotension

Progressive

- Erythematous or massive urticarial rash
- Edema of face, neck, soft tissues

Severe

- Hypotension
- Bronchospasm (wheezing)
- Laryngeal edema (dyspnea, stridor, aphonia, drooling)
- Arrhythmias

Treatment Algorithm

With the onset of any of the above clinical signs, immediately discontinue study medication administration and initiate the following monitoring:

- Continuous electrocardiographic monitoring
- Continuous pulse oximetry
- Measure blood pressure every 5 minutes
- Perform chest auscultation every 5 minutes

- Blood samples need to be collected for Tryptase (29-33) and antibodies. Tryptase samples need to be withdrawn at:
 - 1st sample taken 0.25-3 hours after onset of symptoms
 - 2nd sample taken between 3-6 hours
 - 3rd sample taken 24-48 hours to verify the return to baseline

In the case of progressive or severe hypersensitivity, treat appropriately and withdraw the subject from the study. Treat as detailed below.

Urticaria or edema of the face, neck, or soft tissues

- Epinephrine 1:1000 solution, 0.5 mL subcutaneously, repeat as needed every 5-10 minutes
- Antihistamines
- Corticosteroids

Hypotension (systolic blood pressure (SBP) \leq 90 mmHg)

- Isotonic sodium chloride solution, 1 L every 30 minutes as needed to maintain SBP >90 mmHg
- Epinephrine 1:10,000 solution given IV at 1 μ g/minute initially, then 2-10 μ g/minute to maintain SBP >90 mmHg
- Norepinephrine 4 mg in 1 L 5% dextrose in water given IV at 2-12 μ g/minute to maintain SBP >90 mmHg
- Glucagon 1 mg in 1 L 5% dextrose in water given IV at 5-15 μ g/minute for refractory hypotension

Bronchospasm

- Oxygen by face mask at 6-8 L/minute to maintain oxygen saturation at $>90\%$
- Epinephrine 1:1000 solution, 0.5 mL subcutaneously
- Albuterol 0.5 mL of 0.5% solution in 2.5 mL of sterile saline every 15 minutes up to three doses
- Inhaled beta-agonists
- Corticosteroids

Laryngeal edema

- Epinephrine 1:1000 solution, 0.5 mL subcutaneously, repeat as needed every 5 to 10 minutes
- Corticosteroids

Premedication

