14.4.2 MRI Data

Each subject enrolled in this study will have 2 MRI time points during the course of the trial at Baseline and Month 12 (or early termination). For each time point, the same set of T1 and T2-weighted MRI sequences will be acquired. An imaging manual will be shared with sites to outline the scanning protocol. The exact sequence parameters will be defined based on site's equipment and abilities to provide sufficient image quality and contrast for organ (spleen and liver) detection and quantification, and full spleen and liver coverage in GD subjects. No contrast agent will be used.

An MRI of the abdomen containing the entire spleen and liver will be collected at the Screening visit (Day -25 ± 10) and Week 52 Visit (± 7 days). Volumes of liver and spleen will be evaluated centrally by an independent radiologist. All scans should be submitted within 2 days of acquisition to allow quality review by the central radiologist. The MRI site must confirm the scan is acceptable prior to sending images for central review. The inspection by the site will include complete anatomic coverage of the liver and spleen. Scans that are not accepted by the central radiologist may result in rescan requests. The method of evaluation used for each patient at baseline should remain consistent for the duration of the study. In instances when the scan must be repeated (ie, if upon submission to the central radiologist, quality control issues are identified and communicated to the site) the repeated scan must be evaluated.

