14.4.3.2 Subject Sedation

Pediatric subjects may require sedation in order to obtain the high quality images required. Sites may use standard sedation protocols approved by the institution.

14.4.3.3 Quality Control of Image Data and Site Quality Assurance During the Course of the Study

The image data will be collected and quality inspected by the central radiologist for checking the technical adequacy, the compliance of data acquisition with the imaging guidelines and the

diagnostic quality of the images (their appropriateness for centralized evaluations). If any quality-related issue is detected by the central reviewer this will be communicated to the site.

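### For progressive or severe hypersensitivity below the Grade 3/4 removal threshold, Appendix 14.3 directs withdrawal while Section 6.3.3 and the synopsis leave it to discretion

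*Protocol*

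**What the plan says.** Four places in the protocol bear on this.

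- **Appendix 14.3**, the hypersensitivity evaluation and treatment algorithm, is introduced as something that will be followed. After its list of clinical signs it instructs: "In the case of progressive or severe hypersensitivity, treat appropriately and withdraw the subject from the study".
- **Section 6.3.3, item 2**, refers the reader to Appendices 14.2 and 14.3 and says that a subject with progressive or severe hypersensitivity "will be treated appropriately and may be withdrawn from the study, at the discretion of the treating Investigator and/or Medical Monitor".
- **The synopsis**, under discontinuation, reads: "A subject who experiences progressive hypersensitivity or severe hypersensitivity will be treated appropriately and may be withdrawn from the study". It attaches the same discretion.
- **Appendix 14.2** deals with severe cases only. It sends them to the WHO toxicity criteria and adds that "there may be a discontinuation of treatment according to the protocol".

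Two further provisions set the limits of the point. Item 1 of Section 6.3.3 (also in the synopsis) lists, as a reason for permanent discontinuation, two or more Grade 3 toxicities or at least one Grade 4 toxicity that the Investigator considers associated with the drug. After any discontinuation, Section 6.3.3 has the Investigator "attempt to continue to follow the subject for the full duration of the study or at least for 30 days following discontinuation".

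**The concern.** The same trigger leads to the same action with different force: directed in the appendix, optional in the body and synopsis. Because item 2 points to Appendix 14.3, a site that follows the cross-reference moves from a discretionary rule to a mandatory one, and nothing says which governs.

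The practical case is an Investigator who wishes to keep the subject. That is conceivable: the prescribing information reproduced as Appendix 14.1 asks for risks and benefits to be weighed before re-administration after a severe reaction. Under item 2 the decision is allowed. Under Appendix 14.3 it is a departure from the protocol. A monitor could not classify it, and two sites could treat similar reactions differently while each relied on protocol text. Hypersensitivity is a recognised risk of this drug, so the instruction should be unambiguous.

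A secondary question is what withdrawal means. Appendix 14.3 speaks of leaving the study, whereas Section 6.3.3 expects follow-up after discontinuation. The primary estimand in SAP 2.1.1 uses a treatment-policy strategy and includes data after an intercurrent event where they are collected, so the reading adopted affects whether a Month 12 scan is obtained.

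**Working it through.** No figure in the plan depends on this point, so the check is a comparison of texts.

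**Step 1: the rules side by side.**

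| Place | Trigger | Action | Force |
|---|---|---|---|
| Appendix 14.3 | Progressive or severe | Withdraw from study | Directed |
| Section 6.3.3 item 2 | Progressive or severe | Withdraw from study | Discretionary |
| Synopsis | Progressive or severe | Withdraw from study | Discretionary |
| Appendix 14.2 | Severe only | Stop treatment | Possible, by reference to the protocol |

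The first three rows differ only in force. The fourth defers to the rest of the protocol and sets no rule of its own; it is a passage to align.

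**Step 2: which decisions expose the conflict.**

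- Subject withdrawn: Appendix 14.3 is met, and item 2 is met because it permits withdrawal.
- Subject retained: item 2 is met; Appendix 14.3 is not.

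Only retention brings the two texts into conflict.

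**Step 3: which reactions are already settled by item 1.** Item 1 carries no discretion beyond the attribution to study drug. Signs that Appendix 14.3 calls progressive or severe can be set against the grades in Appendix 14.5:

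| Reaction | Grade in Appendix 14.5 | Does one such event meet item 1? |
|---|---|---|
| Anaphylaxis | Allergy, Grade 4 | Yes, if considered drug-related |
| Bronchospasm needing parenteral medication | Allergy, Grade 3 | No; two or more Grade 3 are required |
| Mild bronchospasm | Allergy, Grade 2 | No |
| Urticaria | Allergy, Grade 2 | No |
| Hypotension needing fluids or other therapy, without hospitalization | Hypotension, Grade 2 | No |
| Edema of the face or neck | No specific entry in the Allergy row | Not by that row |

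Appendix 14.3 places bronchospasm and hypotension among severe signs, and massive urticarial rash and facial edema among progressive ones. A subject can therefore be in a category for which Appendix 14.3 directs withdrawal without meeting item 1. A reaction with two Grade 3 components, or any Grade 4 component, would meet item 1 if attributed to the drug.

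**Step 4: reach into the analysis.** A treated subject who leaves early stays in the full analysis set. SAP 5.3 then uses, in order, the early-termination MRI, the ultrasound change (per clinical judgment), or the baseline value. The per-protocol set loses the subject only if no Month 12 scan exists. Subjects are not replaced (Section 6.3.4), but up to 15 are enrolled to yield at least 9 completers, which leaves room for up to 15 − 9 = 6 losses if enrolment is full.

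**The case against.** The strongest reply is that there is little to resolve: item 2 stands under a heading of reasons for permanent discontinuation, it refers the reader to the stricter appendix, and a site that withdraws the subject complies with everything. Most of this is right, and it narrows the point. It does not remove it, because item 2's own wording is permissive and expressly discretionary, and a cross-reference is not a statement of precedence.

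Four stronger readings are tempting and are not supported.

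- *The two rules can never both be followed.* They can, by withdrawing the subject.
- *Handling of every severe reaction, including anaphylaxis, is in dispute.* Drug-related anaphylaxis falls under item 1 without discretion, so Section 6.3.3 and Appendix 14.3 agree there.
- *Earlier trials show how often the conflict would arise.* The documents report anaphylaxis in 2 of 72 patients and two discontinuations for hypersensitivity among 32 adults in Study PB-06-001. The first counts cases that item 1 covers if they are drug-related; the second counts patients who left, for whom both rules give the same result. Neither counts subjects with a qualifying reaction below item 1 whom an Investigator wished to retain.
- *It is unclear which scan would be analysed, or a third MRI would be needed.* SAP 5.3 uses the early-termination MRI only when the Month 12 visit is missing, so a Month 12 scan takes precedence. Section 9.2.12 lets the Medical Monitor waive early-termination procedures.

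It is also fair to say that the unclear meaning of withdrawal applies to every discontinuation reason in Section 6.3.3. It is secondary here, and worth settling only because the same sentences will be amended.

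**Conclusion.** The contradiction is real and narrow. For progressive or severe hypersensitivity that does not meet item 1 of Section 6.3.3, the protocol both directs withdrawal and leaves it to discretion, and a decision to retain the subject is permitted by one text and a departure from the other.

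Its frequency cannot be quantified from the documents, which give no counts by the Appendix 14.3 categories and none by retention decision. The effect on the primary result is limited: follow-up, early-termination assessments and a missing-data rule are already planned. The reason to correct it is clarity of a safety instruction; the validity of the primary test is not in question.

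The conclusion assumes that the Appendix 14.5 grades are those item 1 relies on, as its cross-reference indicates. It rests on the text of Appendix 14.2 alone, since that appendix's figure is not shown; how infusions with lesser signs are handled is outside this point.

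**What to change.** Reconcile the synopsis, Section 6.3.3 item 2 and Appendix 14.3 so that one rule applies to progressive and severe hypersensitivity, and align the sentence on severe cases in Appendix 14.2 with it. Which rule to adopt is for the sponsor's clinicians; this review takes no position.

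In the same wording, say whether the rule means stopping study drug or leaving the study, so that the follow-up requested in Section 6.3.3 and the treatment-policy estimand in SAP 2.1.1 can be applied as written.

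The cost is amendment wording only. No additional assessments, subjects or changes to the analysis are needed.

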Premedication for subsequent taliglucerase alfa infusions may be considered at the discretion of the Investigator and Medical Monitor for subjects experiencing early clinical signs of hypersensitivity or rash/urticaria that responds promptly to oral antihistamine administration (see also [Appendix 14.2](#) for adjustment of infusion rate). The premedication will be applied according to the following steps as needed to prevent progressive hypersensitivity:

- Antihistamine (H1 blocker: diphenhydramine, hydroxyzine, cetirizine, loratadine, desloratadine) at a standard dose 12 hours and 2 hours before the start of the infusion
- H1 blocker plus H2 blocker (ranitidine, cimetidine, famotidine) at standard doses 12 hours and 2 hours before the start of the infusion
- H1 blocker plus H2 blocker plus prednisone up to 50 mg administered 12 hours and 2 hours before the start of the infusion

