6.7.1. Adverse Events

Treatment-emergent adverse events (TEAE) will be summarized with counts and percentage for safety population (defined in [Section 4](#)) according to Pfizer CDISC standard. All adverse events will be reported in a data listing.

In addition to the system organ class (SOC) and preferred term (PT) defined in the live MedDRA version at the final reporting stage, an additional SOC of hypersensitivity reactions will be summarized using frequency and percentage for each preferred term, including but not limited to:

- Early clinical signs: sensation of warmth and itching, feelings of anxiety or panic;
- Moderate clinical signs: pruritus, flushing, urticaria, chest discomfort, mild hypotension;
- Progressive clinical signs: erythematous or massive urticarial rash;
- Severe clinical signs: hypotension, bronchospasm (wheezing), laryngeal edema (dyspnea, stridor, aphonia, drooling), arrhythmias.

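### Appendix 14.3 puts an erythematous rash that clears promptly under both withdrawal and premedicated continuation, and lists urticaria as Moderate while heading the progressive/severe treatment block with it

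*Protocol*

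**What the plan says.** Appendix 14.3 is presented as the algorithm that sites are to follow during and after infusion. It has four parts that matter here.

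- **Sign list.** Early includes "Sensations of warmth and itching". Moderate lists pruritus, flushing, urticaria, chest discomfort and mild hypotension. Progressive lists "Erythematous or massive urticarial rash" and edema of the face, neck and soft tissues. Severe lists hypotension, bronchospasm, laryngeal edema and arrhythmias.
- **Withdrawal sentence.** "In the case of progressive or severe hypersensitivity, treat appropriately and withdraw the subject from the study". The reader is then directed to the treatments that follow.
- **Treatment block.** Its first heading is "Urticaria or edema of the face, neck, or soft tissues". A later heading defines hypotension as a systolic pressure of 90 mmHg or less.
- **Premedication paragraph.** Whether to premedicate before later infusions is left to the judgment of the site physician together with the medical monitor. The group it covers is defined as those "experiencing early clinical signs of hypersensitivity or rash/urticaria that responds promptly to oral antihistamine administration". The steps are applied "as needed to prevent progressive hypersensitivity".

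Protocol Section 6.3.3 and the synopsis cover the same two upper classes but make withdrawal a matter for the judgment of the investigator or the medical monitor. Section 6.3.3 refers the reader to Appendices 14.2 and 14.3. SAP Section 6.7.1 repeats the class labels, for example "Moderate clinical signs: pruritus, flushing, urticaria, chest discomfort, mild hypotension", under one added hypersensitivity grouping.

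**The concern.** In this appendix the class of a sign decides whether a subject leaves the study or may go on to further infusions. If one skin reaction fits a line with each consequence, two sites that follow the text faithfully can act in opposite ways on the same event. What is at stake is consistent safety handling of a known risk of the drug, and a clear record of why a subject was withdrawn or continued. In a single-arm study of up to 15 subjects with no replacement of withdrawals (Section 6.3.4), each such decision is visible in the results.

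**Working it through.** No figure in the plan underlies this point, so the check is to take each reaction through the lines of Appendix 14.3.

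| Reaction | Sign list | Withdrawal sentence | Treatment block | Premedication paragraph |
|---|---|---|---|---|
| Erythematous rash, clears promptly on oral antihistamine | Progressive | Applies | No heading names rash | Applies |
| Plain urticaria, clears promptly on oral antihistamine | Moderate | Does not apply | First heading names it | Applies |
| Itching | Early | Does not apply | Not named | Applies |
| Pruritus | Moderate | Does not apply | Not named | Not named |
| Hypotension | Moderate if mild, otherwise Severe | Depends on class | 90 mmHg or less | Not named |

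**Rash.** Progressive is the only class in which the word rash appears, and the withdrawal sentence for that class carries no exception. The Premedication paragraph is about subsequent infusions, which a withdrawn subject does not receive in the study. Row one therefore meets two lines with incompatible consequences. The result does not depend on how the Progressive entry is parsed. If it means an erythematous rash of any kind, the overlap is with rash. If both adjectives qualify urticarial rash, the overlap is with urticaria that is erythematous and clears promptly.

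**Urticaria.** The sign list and the Premedication paragraph agree with each other: Moderate, with continuation possible. The treatment heading does not fit them. It omits the qualifier massive, and it stands first in the block that the withdrawal sentence introduces. A site looking up how urticaria is treated finds it only there. This is a mismatch of placement, not an order to withdraw.

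**Itching and pruritus.** One symptom appears in two classes. Neither class leads to withdrawal, and any listed sign triggers the same interruption and monitoring. The only consequence is that a subject recorded with itching is named for premedication while a subject recorded with pruritus is not.

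**Hypotension.** This is a split by severity, so it is not the same entry twice. The gap is that the class list gives no limit for mild. The 90 mmHg value is attached to a treatment heading and is not stated to be the dividing line between Moderate and Severe.

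**Section 6.3.3.** For Progressive and Severe reactions it permits withdrawal, while Appendix 14.3 instructs it. Because Section 6.3.3 cites the appendix, it does not settle the matter.

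**The case against.** The strongest reply is that withdrawal is ordered by class and urticaria is Moderate. The disputed heading is a treatment heading, and it can be read as urticaria or edema located at the face, neck or soft tissues. Other parts of the protocol treat urticaria as manageable: Appendix 14.2 uses an antihistamine for urticaria as an example of a Grade 1 or 2 event responding to treatment, and Appendix 14.5 places urticaria at Grade 2 for allergy, while removal for toxicity in Section 6.3.3 starts at two Grade 3 events or one Grade 4 event. This stands. A reader might infer that plain urticaria is sent to withdrawal, but no line says so.

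It can also be said that premedication is discretionary, limited to prompt responders, and meant for subjects who have not yet progressed. That may well be the intent. It does not remove the rash overlap, because the sign list assigns class by what the reaction looks like, not by how it responds, and no lesser rash is listed.

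Three further inferences are tempting and are not supported.

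- **Itching or hypotension is in two classes, so who is withdrawn is undetermined.** For itching this is wrong, since neither class leads to withdrawal. For hypotension only the limit for mild is missing.
- **The SAP reaction table is undetermined.** SAP 6.7.1 reports frequency and percentage by preferred term, and the class labels organise an open list. Counts by term do not change with class.
- **Power collapses.** The plan's sign-test figure reproduces. With 9 subjects and rejection at 8 or more responders (or 1 or fewer), alpha is 2 × 10/512 = 0.039 and power at 0.91 is 9 × 0.91^8 × 0.09 + 0.91^9 = 0.381 + 0.428 = 0.809. With 8 subjects, 8 of 8 is needed (7 of 8 gives alpha 2 × 9/256 = 0.070), and power is 0.91^8 = 0.470. That drop does not follow from this point. Up to 15 may enrol to yield 9 completers. SAP 5.3 uses early-termination MRI as the Month 12 value in the full analysis set, with ultrasound or baseline carried forward behind it, so a withdrawn subject stays in the count. The primary test is also a Wilcoxon signed rank test, not the sign test.

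**Conclusion.** Appendix 14.3 contradicts itself on rash: an erythematous rash that clears promptly on an oral antihistamine falls under both withdrawal and possible continuation. The urticaria heading is inconsistent with the Moderate class. The itching/pruritus duplication and the undefined limit for mild hypotension are minor.

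The number of subjects affected cannot be derived. The label in Appendix 14.1 reports any hypersensitivity in 21 of 72 patients (29.2%). If that rate carried over, 15 × 0.292 = 4.4 subjects, or 9 × 0.292 = 2.6, would have some reaction. The disputed rash would be an unknown share of these, possibly none. Even on the extreme assumption that every reaction led to withdrawal and all 15 places were filled, the chance of at least 9 completers is 0.88.

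The point therefore rests on consistent handling of a stop-or-continue rule that bears on patient safety. It makes no claim about sample size, power, alpha or the SAP's preferred-term counts.

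**What to change.** Reconcile the sign list, the first treatment heading and the Premedication paragraph of Appendix 14.3 so that the same rash or urticaria does not fall under both withdrawal and continuation. Align the result with Section 6.3.3 and the synopsis, which leave withdrawal to judgment where the appendix instructs it. In the same edit, remove the overlap between itching and pruritus, and state in the class list what separates mild from other hypotension. Which rule applies in each case is for the sponsor's clinicians; this review takes no position on it.

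The cost is protocol wording only. No added subjects, procedures or data fields are needed, and the SAP analyses do not change.
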